In the **implementation phase** (month 7), we will train clinic staff in all eight clinics (study clinics and comparison clinics) on the Ugandan standard of care for diagnosis and treatment of TB. In addition, in the four study clinics, we will provide training on the PredicTB score. This training will include the following elements: (a) background on the PredicTB score and its aim of informing empiric treatment decisions for adult pulmonary TB; (b) provision of materials (paper score sheets and laminated instruction sheets) to enable clinicians to use the PredicTB score; (c) reinforcement that all treatment decisions are ultimately at the discretion of the treating physician; (d) reinforcement that PredicTB is not meant to be a replacement for microbiological testing – that sputum should be sent for microbiological testing in all patients presenting with symptoms of TB, and that any patient with a positive microbiological test should be treated for TB. Prior to this training, we will speak with the head (in-charge) physician at each of the four study clinics to describe the PredicTB score and elicit the physician's recommendations as to the percentage of TB tests that are positive in the clinic (i.e., columns in Figure 1) and the score that should be encouraged as a threshold for same-day empiric treatment initiation. Importantly, this threshold may vary from one clinic to another; our analyses will not explicitly incorporate this threshold as a covariate, but we will explore clinic-by-clinic variation by way of informing any future clinical trial. Furthermore, we will seek the in-charge physician's advice regarding an alternative approach in which patients with high (e.g., >40%) risk could be scheduled for a full treatment course, whereas those with intermediate (e.g., 10-40%) risk could be prescribed a provisional (e.g., 14-day) course, which could be discontinued if microbiological testing for TB was negative and the clinical course [e.g., full resolution in 1-2 days or continued worsening of symptoms despite TB therapy] were inconsistent with a diagnosis of TB. Training in the use of the PredicTB risk score in each clinic will therefore follow the recommendations of each clinic's in-charge physician and will only augment (not supplant) the Ugandan standard of care for TB management. We will re-evaluate these recommendations every three months during site visits (see below) and update training as needed.

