In the **post-implementation phase** (months 7-18), we will encourage all eight clinics (study and comparison clinics) to continue high-quality record-keeping as during the pre-implementation phase. The four study clinics

Figure 2. Study Overview

will be asked to maintain records of the PredicTB score sheets for all patients on whom the score was calculated. We will also perform quarterly site visits that will include the following components:

- Review of the quality of record-keeping and transmittal of records to study staff [all clinics];
- Collection of cost data, including budgetary review and time-and-motion studies [study clinics];
- Assessment of PredicTB reach (proportion of patients receiving same-day empiric treatment initiation), adoption (proportion of clinicians adopting PredicTB), and implementation (proportion of patients in whom PredicTB was used as indicated) [study clinics]; and
- Performance feedback to clinic staff regarding TB diagnosis and treatment outcomes [all clinics].

During this phase, we will also perform mycobacterial culture (using both solid [Lowenstein-Jensen] and liquid [Mycobacteria Growth Indicator Tube, MGIT; BD Diagnostics, Sparks, MD, USA] media) on all sputum specimens from all eight clinics that are Xpert-negative but correspond to adult patients who were empirically initiated for TB. *These culture results will not be used for any of our primary effectiveness analyses* but instead will be used to estimate the sensitivity and specificity of empiric treatment decisions, both with and without the PredicTB score. Specimens will be sent from the central laboratories in which Xpert is performed, rather than from study clinics themselves, so as to minimize interference with study clinic procedures. Nevertheless, culture results will be transmitted back to clinicians to assist with management.

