3.3.4. Analysis Plan

Table 1. Overview of Analysis Plan

Specific Aim	Analytic Goal	Primary Outcomes (1° outcome underlined)	Secondary Analyses	Analytic Strategy
Aim 1	Evaluate PredicTB Effectiveness	Differences in proportions (pre-post): Treatment initiation (1a) Mortality (1b) Loss to follow-up (1b) Difference in differences (study – comparison) (1c)	Adjustment for age, sex, HIV status, treatment history Regression discontinuity	Mixed-effects log-binomial models (clinic as random effect) Parametric regression discontinuity analysis Difference-in-difference ("product term") model
Aim 2	Evaluate PredicTB Implementation	Reach (2a): % same-day empiric treatment Adoption (2b): % providers using PredicTB Implementation (2c): % of encounters using PredicTB as indicated Maintenance (2d): chg in effectiveness over time	Validation with patient surveys Sensitivity/specificity of empiric tx decisions Association with patient level characteristics	Binomial distribution & confidence intervals w/ clustering by clinic Mixed-effects log-binomial models
Aim 3	Estimate PredicTB Impact & Cost-Effectiveness	Projected reduction in 5-year TB mortality (3a) Incremental cost per DALY averted (3b)	Probabilistic sensitivity analyses Uncertainty analyses Unit cost estimation	Markov state-transition model Cost-effectiveness analysis

Aim 1. Evaluate the effectiveness of the PredicTB clinical risk score on clinical outcomes. Our primary analysis will estimate the absolute difference in the proportion of patients with microbiologically confirmed TB (Xpert or smear; study-driven culture results will be excluded) who are initiated on anti-TB treatment within 7 days of submitting an initial sputum specimen for TB diagnosis, comparing the post-initiation period to the pre-initiation period (dark minus light blue in Figure 2). We will estimate this quantity using a multilevel log-binomial

model, with random-effect terms corresponding to each of the four study clinics. We will perform similar analyses for the proportion of patients with TB who complete treatment and die from any cause (Aim 1b).

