Aim 2. Evaluate the implementation of the PredicTB clinical risk score. Using the RE-AIM framework^{64,65} as a guide, we will evaluate the implementation of PredicTB according to its reach (proportion of symptomatic patients initiating same-day empiric treatment, Aim 2a), effectiveness (Aim 1), adoption (proportion of providers managing TB in study clinics who use the PredicTB score, Aim 2b), implementation (proportion of eligible patient encounters in which PredicTB is used as indicated), and maintenance (change in effectiveness between month 7 and 18). We will estimate each of these quantities using data from treatment registers and completed PredicTB score sheets and will validate these estimates on the subset of patients who present to treatment during our quarterly site visits. All analyses will include random effect terms to account for clustering of implementation effects at the clinic level.

Aim 3. Project the long-term impact and cost-effectiveness of PredicTB implementation. Based on our experience of estimating the clinical impact of TB treatment regimens^{66,67} and diagnostic tests^{68,69}, we will construct a Markov model of long-term patient outcomes, informed by data from this study. This model will use estimates from the scientific literature to incorporate probabilities of TB mortality, repeat diagnostic attempts, and effectiveness of partial TB treatment. Our primary impact outcome will be the projected reduction in five-year TB mortality effected by PredicTB implementation. We will expand this model to incorporate estimates of costs (which we will empirically measure during the study, using study tools developed by our team for this purpose^{69,70}). We will follow standard guidance for economic evaluation, including inflation using Uganda's GDP deflator, conversion to a common currency and year (2021 US dollars), discounting of all future costs and effectiveness, and measurement of costs as economic (opportunity) costs.^{71,72} We will perform a probabilistic sensitivity analysis (using beta distributions for parameters with defined upper and lower bounds and gamma distributions for those bounded at zero to infinity) to generate 95% uncertainty ranges. We will construct cost-effectiveness acceptability curves, using \$500 per DALY as a conservative cost-effectiveness threshold^{73,74} but also considering revealed thresholds for competing interventions.

3.3.5. Potential Challenges, Alternative Solutions, and Next Steps.

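### Reach (Aim 2a) counts every same-day empiric start in study clinics after implementation, scored or not and with no planned baseline, so it mixes score uptake with background treatment and clinic thresholds

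*Combined protocol and SAP*

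**What the plan says.** Reach is stated three times. Table 1 in section 3.3.4 has "Reach (2a): % same-day empiric treatment". The Aim 2 text in that section has "reach (proportion of symptomatic patients initiating same-day empiric treatment, Aim 2a". The quarterly site-visit tasks in section 3.3.3 include "Assessment of PredicTB reach (proportion of patients receiving same-day empiric treatment initiation"; that item belongs to the post-implementation phase and is tagged for study clinics only.

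On data, Aim 2 says "We will estimate each of these quantities using data from treatment registers and completed PredicTB score sheets", and study clinics are asked to "maintain records of the PredicTB score sheets for all patients on whom the score was calculated". On analysis, Table 1 gives "Binomial distribution & confidence intervals w/ clustering by clinic" and mixed-effects log-binomial models for Aim 2. It states no contrast between periods or clinic groups for reach; those contrasts belong to Aim 1.

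Each in-charge physician recommends a threshold for same-day empiric treatment. Section 3.3.3 adds: "Importantly, this threshold may vary from one clinic to another". The recommendation is reviewed every three months and is not a model covariate, although variation between clinics will be explored.

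**The concern.** A reader who sees a reach figure carrying the name of the score will take it as the share of patients the score got to. As defined, it is the share started on empiric treatment the same day for any reason. A patient started on clinical judgement with no score sheet counts, and so does one whose score fell below the clinic's threshold. Conversely, a clinic that scores everyone but works with a high threshold can show low reach.

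There is also nothing to set the figure against. Section 3.3.3 leaves all treatment decisions with the clinician, trains all eight clinics on standard of care, and gives all of them quarterly performance feedback. Any of these could produce or change same-day empiric treatment without the score. For Aim 1 the plan recognises this kind of bias and adds a difference-in-differences analysis; for reach it adds nothing comparable.

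At stake is how the implementation findings are read. The study is meant to inform a cluster-randomised trial and, if outcomes do not improve, to explain why. For that, the team needs to know whether low or high reach reflects use of the score, the threshold chosen, or prior habit.

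**Working it through.** The plan gives no expected value, target or precision for reach, so there is no stated figure to reproduce. The check has two parts.

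**1. The definitions side by side.**

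- Numerator: all three definitions say same-day empiric treatment. None mentions a score sheet or a threshold.
- Period and clinics: the site-visit item places reach after implementation, in study clinics.
- Related outcomes: adoption (2b) is the share of providers using the score; implementation (2c) is the share of eligible encounters in which it is used as indicated. Neither is cross-classified with treatment starts. For example, reach of 10% with half of encounters scored could mean that all the starts were scored or that none were, depending on how many scored patients met the threshold.
- Available data: standard registers of sputum submissions and treatment starts are abstracted before and after in all eight clinics, and score sheets are kept in study clinics. The missing baseline is a gap in the analysis plan, not in the data.

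**2. An illustration of what the measure mixes.** All inputs here are assumptions. Let b be the share of patients who would start empirically the same day anyway, u the share scored, and q the share of scored patients who are at or above the threshold and are started because of it. Treating these as independent,

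R = b + u × q × (1 − b).

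| b | u | q | Reach R | R − b | b / R |
|---|---|---|---|---|---|
| 10% | 0% | any | 10.0% | 0 points | 100% |
| 2% | 80% | 10% | 2% + 8% × 0.98 = 9.8% | 7.8 points | 20% |
| 5% | 80% | 10% | 5% + 8% × 0.95 = 12.6% | 7.6 points | 40% |
| 5% | 80% | 30% | 5% + 24% × 0.95 = 27.8% | 22.8 points | 18% |
| 0% | 80% | 10% | 8.0% | 8.0 points | 0% |
| 0% | 80% | 30% | 24.0% | 24.0 points | 0% |
| 10% | 25% | 10% | 10% + 2.5% × 0.90 = 12.25% | 2.25 points | 82% |

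Rows 1 and 2: a clinic that never uses the score and one that scores 80% of patients show nearly the same reach. Rows 3 and 4: with identical background and identical scoring, reach differs by a factor of 27.8/12.6 = 2.2. Rows 5 and 6: with no background at all, the threshold effect remains (24.0/8.0 = 3). Over b from 0 to 10%, u from 25% to 80% and q from 10% to 30%, the background share of reach runs from 0% (any row with b = 0) to 82% (last row).

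**The case against.** The case for leaving the plan alone is substantial. Reach is a descriptive proportion, and nowhere does the plan derive an effect estimate from it; causal contrasts are assigned to Aim 1. Score use is measured separately by 2b and 2c, and 2c is the primary implementation outcome, so a clinic with starts but no scoring would show near-zero values there. Same-day treatment delivered is a legitimate construct for reach, and a clinic with a higher threshold may truly treat fewer patients that day. Section 1 calls same-day empiric treatment for TB uncommon, so the background may be small.

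Most of this stands, and it limits the point. It does not remove it: 2b and 2c are separate proportions and do not show which starts followed a score, and the threshold effect persists at zero background.

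Several stronger readings are tempting but unsupported:

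- That clinics cannot be compared. Thresholds are elicited clinic by clinic, score sheets are kept and exploration of clinic variation is planned, so descriptive comparison is possible.
- That the plan itself documents unscored starts in study clinics, because the culture work assesses empiric decisions with and without the score. That work covers all eight clinics, and the unscored group may simply be the comparison clinics. Unscored starts in study clinics are plausible but not documented.
- That reach is overstated by some given factor. No background rate is stated, and a rate near zero is compatible with the text.
- That reach should be redefined to count only patients scored at or above threshold. That version would still depend on the threshold, and which construct to call reach is debatable.

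**Conclusion.** The point holds as a matter of definition and reporting. Reach includes any background same-day empiric treatment, has no planned baseline or comparison-clinic value, and combines score uptake with a clinic-specific threshold that may change during follow-up. Raw values are therefore not like-for-like between clinics or quarters, and should not be read as the share of patients reached because of PredicTB.

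The size cannot be derived from the documents. The 0% to 82% background share rests on assumed ranges and independence; at a background near zero only the threshold component matters.

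A reader might infer that the study's main conclusions are undermined. They are not: treatment initiation within 7 days (1a) and use of the score as indicated (2c) do not depend on this definition. The change is worth making because it is cheap and makes a stated implementation outcome interpretable.

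**What to change.** Keep the stated proportion and add the following to the Aim 2 analysis text.

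1. Report same-day empiric starts among patients in the presumptive register for the pre and post periods, in study and comparison clinics, by clinic. Identify same-day starts from submission and treatment dates, which the primary outcome already requires. The abstraction list in section 3.3.3 names no field marking a start as empiric, so state the rule used to infer it, and show same-day starts in smear-positive patients separately.
2. Link register entries to score sheets and split post-period study-clinic starts into scored at or above the clinic's threshold(s) in force on that date, scored below, and not scored. Show this beside the proportion of patients scored. Keep a dated log of each clinic's threshold(s), including any risk bands adopted.
3. Attribute to PredicTB only the score-linked starts, or the change from baseline relative to comparison clinics. State the limits of each: a scored patient might have been started anyway, and the comparison rests on four study and four non-randomised comparison clinics.

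The cost is SAP wording, record linkage and the threshold log. No new patient data and no change to clinical management are needed. The downside is that attributable reach may be lower than the raw figure.

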This analysis is subject to bias resulting from both secular trends and non-intervention-related effects. We will therefore also perform a difference-in-differences analysis, comparing pre-post effects in the study clinics to those observed in the comparison (non-PredicTB) clinics (Aim 1c). We have not made this our primary analysis because the comparison clinics are smaller (thereby reducing power) and not randomly allocated – for example, staff in these clinics may be less motivated to change behavior. We will also perform a parametric regression discontinuity analysis to estimate the causal effect of implementing the PredicTB risk score (with the discontinuity occurring at the time of implementation). This analysis, however, has less statistical power, and the shape of the effectiveness curve over time in the post-implementation period may reflect important effects (i.e., we are interested not only in the immediate effect of the intervention but also its maintenance over time).

Sample size considerations. Based on patient volumes in 2019, we anticipate a sample size of 1100 patients with confirmed TB: 550 pre-intervention and 550 post-intervention. Using data from our STOMP-TB study,¹³ we expect that 55% of patients will initiate treatment within 7 days in the pre-intervention period. Assuming a design effect of 1.67 due to clustering by clinic, we will have 80% power to detect a difference if treatment initiation increases to 66% in the post-intervention phase and 97% power if treatment initiation increases to 70% (Figure 3).

[figure not shown]

Figure 3. Study power

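### Maintenance (Aim 2d) does not say which Aim 1 estimate it tracks and has no comparison-clinic contrast within months 7-18, so drift common to all clinics may be inseparable from a change in PredicTB's effect

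*Combined protocol and SAP*

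**What the plan says.** Maintenance is defined twice in Section 3.3.4. The Aim 2 text gives "maintenance (change in effectiveness between month 7 and 18", and Table 1 gives "Maintenance (2d): chg in effectiveness over time". In the same RE-AIM list, effectiveness is identified only as "effectiveness (Aim 1". Aim 1 contains both the study-clinic pre-post difference (1a, primary) and the study-minus-comparison difference in differences (1c).

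On estimation, the Aim 2 text says "We will estimate each of these quantities using data from treatment registers and completed PredicTB score sheets" and "All analyses will include random effect terms to account for clustering of implementation effects at the clinic level". Score sheets are kept only in the study clinics (Section 3.3.3). Table 1 lists the product-term model in the Aim 1 row. The Aim 2 row lists binomial intervals and mixed-effects log-binomial models, with no group-by-time term.

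The primary Aim 1 analysis is a "model, with random-effect terms corresponding to each of the four study clinics". Of that pre-post analysis the plan says "This analysis is subject to bias resulting from both secular trends and non-intervention-related effects", and it adds Aim 1c in response. For months 7-18, Section 3.3.3 schedules quarterly visits that include "Performance feedback to clinic staff regarding TB diagnosis and treatment outcomes [all clinics".

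**The concern.** Maintenance is meant to show whether PredicTB's effect holds, grows or fades after roll-out. Section 3.3.4 says the team cares about this as well as about the immediate effect. A change over time in the study clinics answers that question only if nothing else moves 7-day initiation during those months. The plan itself gives a reason to expect other movement, because performance feedback goes to all eight clinics throughout the period.

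The plan recognises this kind of bias for the pre-post estimate and adds a comparison-clinic contrast, but writes no counterpart for maintenance. With an upward shared drift, a fading effect could look maintained. With a downward drift, a stable effect could look lost. The reading would feed into the case for, and the design of, the larger trial.

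**Working it through.** **1. The plan's own figure.** The documents give no precision or power for 2d, only power for the primary comparison. Inputs from Section 3.3.4: 550 patients per period, 55% before, 66% or 70% after, design effect 1.67. Two-sided alpha of 0.05 is assumed, since none is stated.
- Effective n = 550/1.67 = 329.3 per period.
- Power = Φ{[d − 1/n − 1.96·√(2p̄(1−p̄)/n)] / √[(p₁(1−p₁)+p₂(1−p₂))/n]}, with continuity correction.
- 55% to 66%: (0.11 − 0.0030 − 0.0747)/0.0379 = 0.853, so 80.3% (stated 80%).
- 55% to 70%: (0.15 − 0.0030 − 0.0740)/0.0373 = 1.959, so 97.5% (stated 97%).

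The stated power reproduces, so the same inputs are used below. The point itself does not depend on it.

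**2. What 2d becomes under the primary estimate.**
(late post − pre) − (early post − pre) = late post − early post, in the study clinics. The baseline cancels, on the difference scale or the log-ratio scale. If PredicTB's effect changes by Δ and all clinics drift by D, the study-clinic quantity is Δ + D. The same change in the comparison clinics is D, and subtracting it leaves Δ. For example, with Δ = −11 points (the whole planned gain lost, 66% − 55%) and D = +11, the study-clinic value is 0 and the contrast is −11.

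**3. Whether another planned analysis separates Δ from D.** Aim 1c contrasts the pre-post change between groups and says nothing about change within the post period. The regression discontinuity is placed at implementation, and no comparison series is described for it. With the pre-period in the model it could at most account for a linear trend already under way, not drift that begins afterwards.

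**4. Precision of the month 7 to 18 change.** Assumptions: patients spread evenly over 12 months (variance of month = (12² − 1)/12 = 11.92, SD 3.452), a linear change over 11 months, 66% in study clinics, 55% in comparison clinics, and 275 comparison patients (the number is not in the documents).
- Study clinics: 11 × √(0.66×0.34/550)/3.452 = 6.4 points.
- Comparison clinics: 11 × √(0.55×0.45/275)/3.452 = 9.6 points.
- Contrast: √(6.4² + 9.6²) = 11.5 points. With 400 comparison patients it is about 10, and with 150 about 14.
- If the full design effect applied to the slope, multiply by √1.67 = 1.292: 8.3 points for study clinics and 14.9 for the contrast.

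**5. Illustrative size.** The drift sizes are assumptions. Each figure is the chance that a 95% interval for the study-clinic change excludes zero when Δ = 0, that is Φ(D/SE − 1.96) + Φ(−D/SE − 1.96).

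| Shared drift over the period | Full design effect (SE 8.3) | No design effect (SE 6.4) | Simulation, no design effect |
|---|---|---|---|
| +5 points | 9% | 12% | 13% |
| +10 points | 23% | 34% | 37% |

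The simulation used 3,000 trials, a clinic SD of 4 points, and a linear probability model with clinic terms and robust standard errors. With no drift it gave 5.6%. It runs slightly above the formula mainly because the binomial variance falls as initiation rises above 66%.

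**6. Scale.** A 10-point rise in both groups cancels on the probability scale but not as a ratio: 76/66 = 1.15 against 65/55 = 1.18.

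**The case against.** The strongest reply is that the text does not plan a study-clinic-only maintenance analysis. It refers to Aim 1 as a whole, and Aim 1 includes the difference in differences, so a time-varying version of 1c may be intended. A reader might infer that the plan will count shared drift as PredicTB's effect. The documents do not support that reading. They leave the estimate unstated, and no model with a month term is written. What stands is the omission: nothing says which estimate is tracked, and 1c as worded is pre-post.

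Second, no test or decision rule is attached to 2d. Table 1 lists intervals and models, and the underlined Aim 2 outcome is 2c. A reader might take the percentages above as the plan's false-positive rate; they only illustrate assumed drifts. This objection stands.

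Third, the comparison clinics may not drift in parallel. Section 3.3.1 relaxed the caseload and in-charge willingness criteria for them, and Section 3.3.4 suggests their staff may be less motivated to change. If the study clinics drifted 10 points and the comparison clinics 5, the contrast would still carry 10 − 5 = 5 points. This also stands.

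Fourth, the contrast is weak. For a complete loss of the 11-point gain, power is about 16% (11/11.5 = 0.95 standard errors) against about 40% in the study clinics alone (11/6.4 = 1.71). The change detectable with 80% power is about 2.80 × 11.5 = 32 points. Section 3.3.4 declined to make the comparison-clinic contrast primary because of clinic size and non-random allocation. A reader might infer that the contrast should replace the study-clinic estimate, but those stated reasons argue against that. They do not argue against reporting it alongside, as 1c is reported for the primary outcome.

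**Conclusion.** The point holds as a gap in specification with a conditional consequence. Aim 2d does not name the Aim 1 estimate it tracks, and no planned analysis compares study and comparison clinics within months 7-18. If the primary pre-post estimate is meant, maintenance is algebraically the study clinics' calendar trend, and shared drift cannot be told apart from a change in PredicTB's effect. That step needs no assumption about the size of drift.

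The size does. The illustrative rates (about 9% to 13% at 5 points, about 23% to 37% at 10) rest on assumed linear drift, even accrual and a two-sided 5% criterion that the plan does not set. The documents do not show that drift will occur, and they do not make the larger trial depend on a maintenance criterion. This is a secondary outcome and an inexpensive improvement; it does not touch the primary analysis.

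**What to change.** In Section 3.3.4, Aim 2, and in the Table 1 entry for 2d:

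1. State which Aim 1 estimate 2d tracks.
2. Keep the study-clinic change from month 7 to 18, described as a trend in 7-day initiation.
3. Prespecify beside it, as the secular-trend check parallel to Aim 1c, an eight-clinic model over the post-implementation months with group, time (month or quarter), group-by-time and clinic terms. Report the group-by-time contrast on the probability scale with its confidence interval.
4. State that change will be attributed to PredicTB only as far as both results support it, and that the contrast is read from its interval and not as a powered test.

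The cost is wording and one additional model. Registers are already abstracted in all eight clinics, so no new data are needed. The downside is precision: a standard error of about 11.5 points against 6.4 under the stated assumptions, before any design effect. The contrast also removes only drift that the smaller, non-randomised comparison clinics truly share.
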